3.2 Post Study Access to Therapy

At the conclusion of the study, subjects who continue to demonstrate clinical benefit will be eligible to receive study drug. Study drug will be provided via an extension of the study, a rollover study requiring approval by responsible health authority and ethics committee or through another mechanism at the discretion of the sponsor. The sponsor reserves the right to terminate access to study drug if any of the following occur: a) the marketing application is rejected by responsible health authority; b) the study is terminated due to safety concerns; c) the subject can obtain medication from a government sponsored or private health program; or d) therapeutic alternatives become available in the local market.

3.3 Study Population

For entry into the study, the following criteria MUST be met.

3.3.1 Inclusion Criteria

1) Signed Written Informed Consent

- a) Willing and able to provide informed consent.

2) Target Population

- a) Men and women ≥ 18 years of age.
- b) Histological confirmation of RCC with a clear cell component.
- c) Advanced or metastatic RCC.
- d) Measurable disease as defined by RECIST 1.1 criteria ([Section 5.4](#)).
- e) Must have received at least one but not more than two prior anti-angiogenic therapy regimens (including, but not limited to, sunitinib, sorafenib, pazopanib, axitinib, tivozanib, and bevacizumab) in the advanced or metastatic setting. Prior cytokine therapy (eg, IL-2, IFN- α), vaccine therapy, or treatment with cytotoxics is also allowed.
- f) Must have received no more than three total prior systemic treatment regimens in the advanced or metastatic setting, and must have evidence of progression on or after the last treatment regimen received and within 6 months prior to study enrollment.
- g) Karnofsky Performance Score (KPS) $\geq 70\%$ ([Appendix 2](#)).
- h) Tumor tissue (FFPE archival or recent acquisition) must be received by the central vendor (block or unstained slides) for correlative studies outlined in [Section 5.6.1.1](#) in order to randomize a subject to study treatment. (Note: Fine Needle Aspiration (FNA) and bone metastases samples are not acceptable for submission.)

3) Age and Reproductive Status

- a) Women of childbearing potential (WOCBP) must use method(s) of contraception based on the tables in [Appendix 3](#). For a teratogenic study drug and/or when there is insufficient information to assess teratogenicity (preclinical studies have not been done), a highly effective method(s) of contraception (failure rate of less than 1% per year) is required. The individual methods of contraception should be determined in consultation with the investigator. WOCBP must follow instructions for birth control when the half life of the investigational drug is greater than 24 hours, contraception should be continued for a period of 30 days plus the time required for the investigational drug to undergo five half lives. For women randomized to receive nivolumab, this is equivalent to 23 weeks after discontinuation of treatment. Women randomized to receive everolimus must follow instructions for birth control as per the SmPC or package insert (8 weeks after discontinuation of treatment).
- b) WOCBP must have a negative serum or urine pregnancy test (minimum sensitivity 25 IU/L or equivalent units of HCG) within 24 hours prior to the start of investigational product.
- c) Women must not be breastfeeding.
- d) Men who are sexually active with WOCBP must use any contraceptive method with a failure rate of less than 1% per year. Men that are sexually active with WOCBP must follow instructions for birth control when the half life of the investigational drug is greater than 24 hours, contraception should be continued for a period of 90 days plus the time required for the investigational drug to undergo five half lives. For men randomized to receive nivolumab, this is equivalent to 31 weeks after discontinuation of treatment. Men randomized to receive everolimus must follow instructions for birth control for 14 weeks after discontinuation of treatment.

4) Physical and Laboratory Test Findings

- a) Serum creatinine $\leq 1.5 \times \text{ULN}$ OR CrCl ≥ 40 mL/min (measured or calculated using the Cockcroft-Gault formula):

$$\text{Female CrCl} = \frac{(140 - \text{age in years}) \times \text{weight in kg} \times 0.85}{72 \times \text{serum creatinine in mg/dL}}$$

$$\text{Male CrCl} = \frac{(140 - \text{age in years}) \times \text{weight in kg} \times 1.00}{72 \times \text{serum creatinine in mg/dL}}$$

3.3.1.1 ***Inclusion Criteria for Entering the Nivolumab Extension Phase - Subjects Previously Randomized to Everolimus***

1) Signed Written Informed Consent

- a) Subjects must have signed and dated an IRB/IEC approved written Informed Consent Form in accordance with regulatory and institutional guidelines. This must be obtained before the performance of any protocol-related procedures that are not part of normal subject care.
- b) Subjects must be willing and able to comply with scheduled visits, treatment schedule, laboratory tests and other requirements of the study.

2) Target Population

- a) Subjects previously randomized to everolimus treatment (Arm B) on the CA209025 study.
- b) Prior anti-cancer therapy, including everolimus and palliative radiotherapy, must have been completed at least 14 days prior to first dose of nivolumab.
- c) All toxicities attributed to prior anti-cancer therapy other than alopecia and fatigue must have resolved to Grade 1 or baseline prior to first dose of nivolumab.
- d) Laboratory values must meet the following criteria and should be obtained within 14 days prior to first dose of nivolumab:
 - i) $WBC \geq 2000/\mu L$
 - ii) $Neutrophils \geq 1500/\mu L$
 - iii) $Platelets \geq 100 \times 10^3/\mu L$
 - iv) $Hemoglobin \geq 9.0 \text{ g/dL}$
 - v) Serum creatinine $\leq 1.5 \times \text{ULN}$ or creatinine clearance (CrCl) $\geq 40 \text{ mL/minute}$ (using Cockcroft/Gault formula):
$$\text{Female CrCl} = \frac{(140 - \text{age in years}) \times \text{weight in kg} \times 0.85}{72 \times \text{serum creatinine in mg/dL}}$$
$$\text{Male CrCl} = \frac{(140 - \text{age in years}) \times \text{weight in kg} \times 1.00}{72 \times \text{serum creatinine in mg/dL}}$$
 - vi) $AST/ALT \leq 3.0 \times \text{ULN}$ ($\leq 5 \times \text{ULN}$ for subjects with liver metastases)
 - vii) Total Bilirubin $\leq 1.5 \times \text{ULN}$ (except subjects with Gilbert Syndrome, who can have total bilirubin $< 3.0 \text{ mg/dL}$).

3.3.2 Exclusion Criteria

1) Target Disease Exceptions

- a) Any history of or current CNS metastases. Baseline imaging of the brain by MRI or CT scan is required within 30 days prior to the first dose of study drug.

2) Medical History and Concurrent Diseases

- a) Prior treatment with an mTOR inhibitor (including, but not limited to, everolimus, temsirolimus, sirolimus, and ridaforolimus).
- b) Any active known or suspected autoimmune disease. Subjects with vitiligo, type I diabetes mellitus, residual hypothyroidism due to autoimmune condition only requiring hormone replacement, psoriasis not requiring systemic treatment, or conditions not expected to recur in the absence of an external trigger are permitted to enroll.
- c) Any condition requiring systemic treatment with either corticosteroids ($> 10 \text{ mg}$ daily prednisone equivalent) or other immunosuppressive medications within 14 days prior to the first dose of study drug. Inhaled steroids and adrenal replacement steroid doses $> 10 \text{ mg}$ daily prednisone equivalent are permitted in the absence of active autoimmune disease.
- d) Uncontrolled adrenal insufficiency.

- e) Any known active chronic liver disease.
- f) Prior malignancy active within the previous 3 years except for locally curable cancers that have been apparently cured, such as basal or squamous cell skin cancer, superficial bladder cancer, or carcinoma in situ of the prostate, cervix or breast.
- g) Known history of testing positive for human immunodeficiency virus (HIV) or known acquired immunodeficiency syndrome (AIDS).
- h) Any positive test for hepatitis B or hepatitis C virus indicating acute or chronic infection.
- i) Known medical condition (eg, a condition associated with diarrhea or acute diverticulitis) that, in the investigator's opinion, would increase the risk associated with study participation or study drug administration or interfere with the interpretation of safety results.
- j) Prior treatment with an anti-PD-1, anti-PD-L1, anti-PD-L2, anti-CD137, or anti-CTLA-4 antibody, or any other antibody or drug specifically targeting T-cell co-stimulation or checkpoint pathways.
- k) Major surgery (eg, nephrectomy) less than 28 days prior to the first dose of study drug. Minor surgery less than 14 days prior to the first dose of study drug.
- l) Anti-cancer therapy less than 14 days prior to the first dose of study drug (less than 28 days for bevacizumab) or palliative, focal radiation therapy less than 14 days prior to the first dose of study drug.
- m) Presence of any toxicities attributed to prior anti-cancer therapy other than alopecia that have not resolved to Grade 1 (NCI CTCAE version 4) or baseline before administration of study drug.
- n) Concurrent use of any medications or substances known to be moderate CYP3A4 or P-gP inhibitors or strong CYP3A4 inhibitors or inducers ([Appendix 4](#)). Although corticosteroids are considered to be strong inducers of CYP3A4, physiologic replacement doses of corticosteroids are allowed at study entry ([Section 3.4.3](#)).
- o) Presence of a malabsorption syndrome, gastrointestinal disorder, or gastrointestinal surgery that could affect the absorption of everolimus.

3) Physical and Laboratory Test Findings

- a) All baseline laboratory requirements should be obtained within 14 days prior to randomization
 - i. WBC < 2000/ μ L
 - ii. Neutrophils < 1500/ μ L
 - iii. Platelets < 100 x 10³/ μ L
 - iv. Hemoglobin < 9.0 g/dL
 - v. AST > 3.0 x ULN
 - vi. ALT > 3.0 x ULN
 - vii. Bilirubin > 1.5 x ULN (except subjects with Gilbert Syndrome, who can have total bilirubin < 3.0 mg/dL)
 - viii. Fasting serum glucose > 1.5x ULN
 - ix. Fasting serum cholesterol > 300 mg/dL or >7.75 mmol/L

- x. Fasting triglycerides > 2.5x ULN

4) Allergies and Adverse Drug Reaction

- a) History of severe hypersensitivity reaction to any monoclonal antibody.

5) Sex and Reproductive Status

- a) WOCBP who are pregnant or breastfeeding
- b) Women with a positive pregnancy test at enrollment or prior to administration of study medication

6) Other Exclusion Criteria

- a) Prisoners or subjects who are involuntarily incarcerated.
- b) Subjects who are compulsorily detained for treatment of either a psychiatric or physical (eg, infectious disease) illness.

Eligibility criteria for this study have been carefully considered to ensure the safety of the study subjects and to ensure that the results of the study can be used. It is imperative that subjects fully meet all eligibility criteria.

**3.3.2.1 Exclusion Criteria for Entering the Nivolumab Extension Phase -
Subjects Previously Randomized to Everolimus**

1) Medical History and Concurrent Diseases

- a) Subjects with active, known or suspected autoimmune disease. Subjects with type I diabetes mellitus, hypothyroidism only requiring hormone replacement, skin disorders (such as vitiligo, psoriasis) not requiring systemic treatment, or conditions not expected to recur in the absence of an external trigger are permitted to enroll.
- b) Subjects with a condition requiring systemic treatment with either corticosteroids (> 10 mg daily prednisone equivalent) or other immunosuppressive medications within 14 days prior to the first dose of nivolumab. Corticosteroids with minimal systemic absorption (for example, topical, inhalational, or as specified in [Section 3.4.3](#)), and adrenal replacement steroid doses > 10 mg daily prednisone or equivalent are permitted in the absence of active autoimmune disease.
- c) Subjects must have recovered from the effects of major surgery or significant traumatic injury at least 28 days prior to the first dose of nivolumab.
- d) Prior treatment with an anti-PD-1 or anti-PD-L1 therapy.
- e) Uncontrolled adrenal insufficiency.

2) Physical and Laboratory Test Findings

- a) Known history of testing positive for human immunodeficiency virus (HIV) or known acquired immunodeficiency syndrome (AIDS).
- b) Known positive test for Hepatitis B virus or Hepatitis C virus indicating acute or chronic infection.

3.3.3 Women of Childbearing Potential

A Woman of Childbearing Potential (WOCBP) is defined as any female who has experienced menarche and who has not undergone surgical sterilization (hysterectomy or bilateral oophorectomy) or is not postmenopausal. Menopause is defined clinically as 12 months of amenorrhea in a woman over age 45 in the absence of other biological or physiological causes. In addition, women under the age of 62 must have a documented serum follicle stimulating hormone, (FSH) level > 40 mIU/mL. Women treated with hormone replacement therapy, (HRT) are likely to have artificially suppressed FSH levels and may require a washout period in order to obtain a physiologic FSH level. The duration of the washout period is a function of the type of HRT used:

- 1 week minimum for vaginal hormonal products, (rings, creams, gels)
- 4 week minimum for transdermal products
- 8 week minimum for oral products
- Other parenteral products may require washout periods as long as 6 months

3.4 Concomitant Treatments

3.4.1 Prohibited and/or Restricted Treatments

The following medications are prohibited during the study:

- Immunosuppressive agents (except to treat a drug-related adverse event)
- Systemic corticosteroids > 10 mg daily prednisone equivalent (except as stated in [Section 3.4.3](#) or to treat a drug-related adverse event)
- Any concurrent antineoplastic therapy (ie, chemotherapy, hormonal therapy, immunotherapy, extensive radiation therapy, or standard or investigational agents for treatment of cancer).
- Strong CYP3A4 inhibitors ([Appendix 4](#))

Supportive care for disease-related symptoms may be offered to all subjects on the trial.

Palliative (limited-field) radiation therapy and palliative surgical resection are permitted, if the following criteria are met:

1. The lesion being considered for palliative radiation is not a target lesion.
2. The subject will be considered to have progressed at the time of palliative therapy and must meet criteria to continue with treatment beyond progression ([Section 4.3.6](#))
3. The case is discussed with the BMS medical monitor or study director.

Surgical resection of lesions is otherwise not permitted.

3.4.2 Other Restrictions and Precautions

Live vaccines should be avoided, whenever possible, while on study treatment.

All subjects (either treatment arm) should avoid moderate CYP3A4 and/or PgP inhibitors and strong CYP3A4 inducers ([Appendix 4](#)). This includes grapefruit, grapefruit juice, and other foods that are known to inhibit cytochrome P450 and PgP activity, as well as St. John's Wort (*Hypericum perforatum*), which is a CYP3A4 inducer. If subjects receiving everolimus do require moderate CYP3A4 and/or PgP inhibitors or strong CYP3A4 inducers during the course of study drug treatment, dose modifications should occur as outlined in [Sections 4.3.2.2](#) and [4.3.2.4](#).

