Hepatic or gastrointestinal events were managed with treatment interruption and administration of corticosteroids, and were generally completely reversible. Endocrine events were managed with replacement therapy. Several subjects in these categories successfully reinitiated treatment with BMS-936558. Drug-related pneumonitis occurred in 3% of subjects; Grade ≥ 3 pneumonitis developed in 3 subjects (1%). No clear relationship between the occurrence of pneumonitis and tumor type, dose level, or the number of doses received was noted. Early-grade pneumonitis was generally reversible with treatment discontinuation and corticosteroid administration. In three subjects, infliximab and/or mycophenolate were utilized for additional immunosuppression, with unclear effectiveness. There were three (1%) drug-related deaths due to pneumonitis.

In two of these cases, the subject did not receive the early and aggressive intervention (including systemic corticosteroid therapy) that is likely key in the management of this toxicity, while in the third case, other anti-cancer agents (erlotinib and vinorelbine) may have contributed to the fatal event.

Preliminary new non-clinical safety findings of adverse pregnancy outcomes and infant losses in the absence of overt maternal toxicity have been reported.⁴³ The findings of increased late stage pregnancy loss and early infant deaths/euthanasia in nivolumab exposed pregnant monkeys suggest a potential risk to human pregnancy if there is continued treatment with nivolumab during pregnancy.

Opportunistic Infections Related to Immunosuppression

As of 03-Apr-2013, three subjects on nivolumab (BMS-936558) clinical trials have developed opportunistic infections (2 cases of Aspergillus, and 1 case of Pneumocystis jiroveci) after receiving prolonged treatment with high dose steroids for nivolumab-related adverse events without antifungal prophylaxis. Details of these cases are available in the BMS-936558 Investigator Brochure.

Because of the potential for opportunistic infections with prolonged high dose corticosteroid administrations, the following recommendations should be considered for subjects with inflammatory events expected to require more than 4 weeks of corticosteroids or other immunosuppressants:

- Antimicrobial/antifungal prophylaxis per institutional guidelines to prevent opportunistic infections such as Pneumocystis jiroveci, bacterial and fungal infections.

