1.4.5.3 Clinical Pharmacology Summary

Single dose pharmacokinetics (PK) of nivolumab (BMS-936558) was evaluated in subjects with multiple tumor types in CA209001 whereas multiple dose PK is being evaluated in subjects in CA209003. In addition, a preliminary population pharmacokinetic (PPK) model has been developed with data from ~ 350 subjects from CA209001, CA209002, and CA209003.

Single dose PK of nivolumab (BMS-936558) was evaluated in 39 subjects with multiple tumor types in study MD1106-01 in the dose range of 0.3 to 10 mg/kg. The median T_{max} across single doses ranged from 1.6 to 3 hours with individual values ranging from 0.9 to 7 hours. The PK of nivolumab (BMS-936558) is linear in the range of 0.3 to 10 mg/kg with dose- proportional increase in C_{max} and $AUC(INF)$ with low to moderate inter-subject variability observed at each dose level (ie, CV ranging from 7 to 45%). Geometric mean clearance (CL) after a single intravenous (IV) dose ranged from 0.13 to 0.19 mL/h/kg, while mean volume of distribution (V_z) varied between 83 to 113 mL/kg across doses. The mean terminal T_{-HALF} of nivolumab (BMS-936558) is 17 to 25 days, which is consistent with half life of endogenous IgG4, indicating that the elimination mechanism of nivolumab (BMS-936558) may be similar to IgG4. Both elimination and distribution of nivolumab (BMS-936558) appear to be independent of dose in the dose range studied. Additional details are provided in the Investigator Brochure.

A preliminary PPK model was developed by nonlinear mixed effect modeling using data from 350 subjects from CA209001, CA209002, and CA209003. The body weight normalized dosing produces approximately constant trough concentrations over a wide range of body weights, and hence is appropriate for future clinical trials of BMS-936558.

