4.3 Selection and Timing of Dose for Each Subject

Subjects in Arm A will receive treatment with nivolumab as a 60 (\pm 10) minute IV infusion on Day 1 and 15 (\pm 2 days) of a treatment cycle. Cycles will be of a 28 (\pm 2 days) duration. Dosing calculations should be based on the actual body weight assessed at either:

- The day of dosing
- The start of each cycle
- Weight at Cycle 1 Day 1 and if the subject's weight on the day of dosing differs by \geq 10% from the weight used to calculate the dose, the dose must be recalculated.

All doses should be rounded to the nearest milligram. The screening body weight may be used for dosing of cycle 1. There will be no nivolumab dose escalations or reductions allowed. Subjects may be dosed no less than 12 days from the previous dose. If a subject cannot receive the 2nd dose of the cycle within the 28 day period it will be omitted and the next dose received will be considered Day 1 of the next cycle

Subjects in Arm B will receive treatment with everolimus 10 mg as a daily oral dose. Cycles will be of a 28 day (\pm 2 days) duration. If everolimus dosing is stopped for \leq 7 days during a cycle, the cycle may be extended to complete the remaining doses. Everolimus dose reductions or escalations are allowed as per the approved product label ([Sections 4.3.2.2 and 4.3.2.4](#)).

On both arms, treatment may be delayed for up to 6 weeks from the last dose. Delays longer than 6 weeks are allowed only in cases where a prolonged steroid taper is required to manage drug-related adverse events or, in some cases, if the delay was due to a non-drug related cause. Prior to re-initiating treatment in a subject with a dosing interruption lasting $>$ 6 weeks, the BMS medical monitor or study director **must** be consulted.

Treatment compliance will be monitored by drug accountability as well as the subject's medical record and eCRF.

Subjects will be monitored continuously for AEs while on study. Treatment modifications (eg, dose delay) will be based on specific laboratory and adverse event criteria.

In some cases, the natural history of AEs associated with immunotherapy can differ from and be more severe than AEs caused by agents belonging to other therapeutic classes. Early recognition and management may mitigate severe toxicity. Evaluation and management guidelines for the following types of adverse events were developed to assist investigators and can be found in the Investigator Brochure:

- Pulmonary toxicity

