- Diarrhea or colitis
- Endocrinopathies
- Hepatotoxicity (including asymptomatic LFT elevations)
- Nephrotoxicity

For patients requiring more than 4 weeks of corticosteroid or other immunosuppressive agents to manage the adverse event, please consider recommendations provided in [section 1.4.5.1](#)

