4.3.2.2 Everolimus Dose Reductions

Everolimus dose reductions are permitted as per the approved product label.

Everolimus dose reductions should be considered for any severe or intolerable drug-related adverse event. If dose reduction is required in the management of an adverse event, the suggested initial reduced dose as per the product label is 5 mg.

For this protocol, the following specific drug-related adverse events require dose reduction if treatment is re-started after requisite dose delay ([Section 4.3.1.2](#)):

- Grade 2 or 3 pneumonitis
- Grade 3 infection
- Grade 3 stomatitis

In addition, as per the approved product label, dose reduction should occur if everolimus is co-administered with moderate CYP3A4 and/or PgP inhibitors ([Appendix 4](#)). Subsequent everolimus dose increases may be considered based on patient tolerance. If the moderate inhibitor is discontinued, a washout period of approximately 2 to 3 days should be allowed before the everolimus dose is increased. If the moderate inhibitor is discontinued, the everolimus dose should be returned to the dose used prior to initiation of the moderate CYP3A4 and/or PgP inhibitor. Additional information regarding everolimus dose escalation is provided in Section 4.3.2.4.

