4.3.4 Discontinuation Criteria

4.3.4.1 Discontinuation Criteria for Nivolumab

Nivolumab administration should be discontinued for the following:

- Any Grade ≥ 2 drug-related uveitis, eye pain, or blurred vision that does not respond to topical therapy and does not improve to Grade 1 severity within the re-treatment period OR requires systemic treatment
- Any Grade 3 non-skin, drug-related adverse event lasting > 7 days, with the following exceptions for laboratory abnormalities, drug-related bronchospasm, hypersensitivity reactions, and infusion reactions:
 - Grade 3 drug-related laboratory abnormalities do not require treatment discontinuation except:
 - ◆ Grade 3 drug-related thrombocytopenia > 7 days or associated with bleeding requires discontinuation
 - ◆ Any drug-related liver function test (LFT) abnormality that meets the following criteria require discontinuation:
 - AST or ALT > 5 - 10 x ULN for > 2 weeks
 - AST or ALT > 10 x ULN
 - Total bilirubin > 5 x ULN
 - Concurrent AST or ALT > 3 x ULN and total bilirubin > 2 x ULN
 - Grade 3 drug-related bronchospasm, hypersensitivity reaction, infusion reaction, uveitis or pneumonitis of any duration requires discontinuation
- Any Grade 4 drug-related adverse event or laboratory abnormality, except for the following events which do not require discontinuation:
 - Grade 4 neutropenia ≤ 7 days
 - Grade 4 lymphopenia or leukopenia
 - Isolated Grade 4 electrolyte imbalances/abnormalities that are not associated with clinical sequelae and are corrected with supplementation/appropriate management within 72 hours of their onset
- Any dosing interruption lasting > 6 weeks with the following exceptions:
 - Dosing interruptions to allow for prolonged steroid tapers to manage drug-related adverse events are allowed. Prior to re-initiating treatment in a subject with a dosing interruption lasting > 6 weeks, the BMS medical monitor or study director must be consulted. Tumor assessments should continue as per protocol even if dosing is interrupted.
 - Dosing interruptions > 6 weeks that occur for non-drug-related reasons may be allowed if approved by the BMS medical monitor or study director. Prior to re-initiating treatment in a subject with a dosing interruption lasting > 6 weeks, the BMS medical monitor or study director must be consulted. Tumor assessments should continue as per protocol even if dosing is interrupted.

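### CYP3A4/PgP drug restrictions justified only for everolimus also bind nivolumab subjects and narrow their antifungal options

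*Protocol*

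**What the plan says.** Two on-study rules apply.

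- Section 3.4.1 puts "Strong CYP3A4 inhibitors" on the list of medications prohibited during the study. The bullets for immunosuppressants and systemic corticosteroids each make an exception for treating a drug-related adverse event. This bullet makes none, and it is not limited by arm or phase.
- Section 3.4.2 is advisory but names both arms: "All subjects (either treatment arm) should avoid moderate CYP3A4 and/or PgP inhibitors and strong CYP3A4 inducers". It then sets out what to do if such a drug is needed, but only for subjects receiving everolimus, and the answer is dose modification.

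The reasons appear in the everolimus dosing sections. Section 4.3.2.2 says that "dose reduction should occur if everolimus is co-administered with moderate CYP3A4 and/or PgP inhibitors", and Section 4.3.2.4 allows the everolimus dose to rise from 10 mg to 20 mg daily with a strong inducer. On nivolumab, Section 1.4.5.3 describes a half-life consistent with endogenous IgG4, "indicating that the elimination mechanism of nivolumab (BMS-936558) may be similar to IgG4".

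On infection risk, Section 1.4.5.1 reports three subjects in nivolumab trials (two with Aspergillus, one with Pneumocystis jiroveci) who developed opportunistic infections after prolonged high-dose steroids without antifungal prophylaxis. For subjects expected to need more than 4 weeks of steroids or other immunosuppressants, it asks sites to consider "Antimicrobial/antifungal prophylaxis per institutional guidelines to prevent opportunistic infections such as Pneumocystis jiroveci, bacterial and fungal infections". Section 4.3 points back to this advice: "For patients requiring more than 4 weeks of corticosteroid or other immunosuppressive agents to manage the adverse event, please consider recommendations provided in" Section 1.4.5.1.

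**The concern.** A restriction that exists to protect everolimus exposure has been written so that it also binds subjects who take no everolimus. For them the protocol states no benefit from it, and it has a cost. It restricts several common antifungals in the setting where the protocol itself warns of opportunistic infection.

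A site treating a nivolumab subject through a long steroid taper, under an institutional guideline that uses a listed azole, would have to choose another agent or depart from 3.4.1 or 3.4.2. What is at stake is a small matter of subject safety and the coherence of the instructions to sites, not the statistical inference.

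**Working it through.** No arithmetic beyond simple counting applies. The check sets the relevant provisions side by side.

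**1. Who is covered.** Section 3.4.2 includes Arm A in so many words. Section 3.4.1 includes it by having no limit. With 1:1 randomization of 822 subjects, planned Arm A is 822 / 2 = 411. No sentence applies either rule to the extension by name; it is caught only by the general wording of the two sections.

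**2. What reason is given.**

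| Provision | Subject of the provision |
|---|---|
| 3.4.2, action if a restricted drug is needed | Subjects receiving everolimus |
| 4.3.2.2, moderate inhibitors | Everolimus dose reduction |
| 4.3.2.4, strong inducers | Everolimus dose increase |
| 1.4.5.3, nivolumab pharmacology | IgG4-like elimination; no CYP3A4 or PgP interaction stated |

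Each stated interaction consequence belongs to everolimus.

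**3. Which antifungals are affected (Appendix 4).**

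| List | Drugs listed | Azole antifungals among them | Effect |
|---|---|---|---|
| Strong CYP3A4 inhibitors | 13 | 4 (ketoconazole, itraconazole, posaconazole, voriconazole) | Prohibited, 3.4.1 |
| Moderate CYP3A4/PgP inhibitors | 8 | 1 (fluconazole) | To be avoided, 3.4.2 |

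So 4 + 1 = 5 azoles are affected. The firm bar is the one in 3.4.1; among these antifungals, the advisory wording of 3.4.2 reaches only fluconazole.

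**4. Whether affected subjects can still be on study therapy.** They can. Section 4.3 states: "Delays longer than 6 weeks are allowed only in cases where a prolonged steroid taper is required to manage drug-related adverse events". The same sentence makes a further allowance for certain delays that the drug did not cause. Section 4.3.4.1 confirms that "Dosing interruptions to allow for prolonged steroid tapers to manage drug-related adverse events are allowed", and Section 4.3.3.1 provides for resuming afterwards. If the rules are read as applying while a subject is on study therapy, the group chiefly affected is nivolumab subjects interrupted for a prolonged taper who intend to resume. Subjects who have permanently stopped are outside it.

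**5. The extension.** Section 3.3.1.1 requires everolimus to have ended at least 14 days before the first nivolumab dose. Section 3.3.2.1 has no counterpart to exclusion 2n of Section 3.3.2, which bars these drugs at original entry. A subject could therefore qualify for the extension while taking a strong inhibitor that 3.4.1 then prohibits.

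**6. A further sign that the scope is too wide.** Appendix 4 lists corticosteroids among the strong CYP3A4 inducers. Read literally, 3.4.2 advises Arm A subjects to avoid the steroids that 3.4.1 allows for a drug-related adverse event.

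**The case against.** The strongest reply is that this is a deliberate choice and contradicts nothing. The authors named both arms, and a protocol need not justify each concomitant-medication rule. Section 1.4.5.1 only asks that prophylaxis be considered, leaves the agent to institutional guidelines and names no azole, so a site can comply with both instructions by using an agent outside Appendix 4. The 3.4.2 wording is advisory. No equivalent dose-modification route could be written for nivolumab, because its dose may not be changed. Further pharmacology sits in the Investigator Brochure, which is not at hand. Section 9.1.1 already permits a deviation to eliminate an immediate hazard.

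Much of this stands. The choice is narrowed rather than removed, and there is no outright contradiction. The lack of a nivolumab dose-modification route is not a missing safeguard. Whether a reason exists outside the protocol cannot be settled here; the point is that the protocol gives none.

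Three things do not answer the concern:

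- **Keeping the arms alike** is never offered as the reason for this rule. Where the protocol applies a rule to both arms to prevent bias, as for treatment beyond progression in Section 1.4.6.6, it says so. The trial is open-label with different dose rules by arm, and the extension follows the analysis now treated as final.
- **Not knowing the arm at entry** justifies criterion 2n, not a rule that continues after randomization.
- **The deviation clause** fits preventive treatment poorly, since prophylaxis is rarely a response to an immediate hazard.

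A simpler alternative would be to add an adverse-event exception to the 3.4.1 bullet for both arms. That would open strong inhibitors to everolimus subjects, for whom Section 4.3.2.2 gives a dose rule only for moderate inhibitors.

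**Conclusion.** The concern holds as a minor, cheap improvement. The on-study CYP3A4/PgP restrictions reach Arm A expressly and the extension by default wording. Their stated justification is confined to everolimus, and they limit the use of five azole antifungals where the protocol asks for prophylaxis to be considered.

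The size is a count of text, not an effect. The rules formally cover about 411 planned Arm A subjects plus extension entrants, but the group that matters is far smaller. The protocol does not say how many subjects would need more than 4 weeks of steroids and remain on nivolumab, so no number is estimated. There is no effect on type I error, power or the OS conclusion.

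The conclusion rests on the protocol text alone and on reading the restrictions as applying during study therapy.

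**What to change.** Limit the on-study rules to everolimus:

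- **3.4.1 bullet:** *Strong CYP3A4 inhibitors (Appendix 4), for subjects receiving everolimus only.*
- **3.4.2, first sentence:** make *Subjects receiving everolimus* its subject, in place of all subjects in either arm.
- **3.4.2, new sentence:** *After randomization these CYP3A4/PgP restrictions do not apply to subjects in Arm A or in the nivolumab extension phase; for antifungal prophylaxis during prolonged steroid treatment see Section 1.4.5.1.*
- **Appendix 4 notes:** add the same everolimus limit.

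Leave the steroid limits in 3.4.1 and 3.4.3 unchanged. Leave screening criterion 2n unchanged too, because the arm is unknown at that point. The new sentence exempts only Arm A and the extension, so an Arm B subject in an everolimus interruption who may resume stays covered.

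The cost is a few lines of wording and one cross-reference. The downside is that concomitant-medication rules then differ by arm after randomization, which is a small price in a trial that is already open-label.
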